1.3. Interim Analysis

The objective of the interim analysis is to evaluate efficacy and safety data in Stage 1 for all 3 cohorts. The interim analysis will be conducted at the end of Stage 1, which is expected to be 6 months after the last subject is enrolled in each NHL subtype, or earlier if emerging data allows.

At the interim analysis, the primary efficacy endpoint of ORR will be evaluated and the major secondary endpoints of DoR, PFS, OS and time to response will be assessed. The detailed analyses of efficacy are described in Section 4. Safety evaluation at the interim analysis will focus on assessment of cumulative interim safety data, specifically on assessment of study treatment discontinuation, adverse events, Grade 3 or 4 adverse events, adverse events related to study treatment, serious adverse events, adverse events leading to study treatment discontinuation, infusion-related reactions, deaths due to adverse event, and clinical laboratory parameters (hematology and chemistry). The detailed analyses of safety are described in Section 5.

1.4. Treatment Allocation and Blinding

After determination of eligibility, subjects will be enrolled to the study. No randomization will be used in this study.

As this is an open study, blinding procedures are not applicable.

2. GENERAL ANALYSIS DEFINITIONS

2.1. Visit Windows

Any analysis that uses time-to-event data will be based on the exact determination of time from first dose of daratumumab to the date of the event. For the calculation of time-to-event and duration-of-event variables, the difference between the start date and the end date plus 1 day will be used.

For analyses of data by cycle, if data are collected by date (ie, AE onset), the corresponding study evaluations will be assigned to actual sequential cycles, which are derived from the study treatment administration data. The start date of a particular cycle is defined as the date of the first dose of daratumumab of that cycle, and the end date of a cycle is the start date of the next cycle minus 1. For the last cycle, the end date is defined as the end of treatment visit date or the minimum of last study treatment date plus 30 days or subsequent anticancer therapy minus 1 day, if the end of treatment visit date is not available.

In general, if data (eg, laboratory and vital sign etc) are collected by cycle, the nominal cycle will be used to summarize data.

2.2. Pooling Algorithm for Analysis Centers

All participating centers in the study will be pooled together for analyses.

2.3. Analysis Sets

The following analysis sets are defined.

- All treated analysis set: is defined as subjects who received at least one non-zero dose of daratumumab.
- Pharmacokinetics-evaluable: is defined as subjects who received at least one non-zero dose of daratumumab and had at least 1 pharmacokinetic sample concentration value after the first infusion. All pharmacokinetics analyses are based on the pharmacokinetic evaluable population.

2.4. Study Treatment and Study Drug

In this study, Study treatment/Study drug refers daratumumab.

2.5. Study Treatment Dosing Date

Study treatment dosing date is the date on which a subject actually received study treatment (partial or complete) and will be recorded in the study treatment administration dataset. The first study treatment date is defined as the earliest date of non-zero dose of daratumumab. The last study treatment date is defined as the latest date of non-zero dose of the daratumumab.

2.6. Treatment Cycle

A subject is considered as treated in a cycle if he/she receives any nonzero dose of daratumumab in that cycle.

2.7. Baseline Measurement

Baseline measurement is defined as the closest non-missing measurement taken on or prior to the date of first study agent administration (including time if available). If the first study treatment date is missing, the corresponding visit date should be used.

2.8. Imputation of Partial Dates

Unless specified otherwise, no data imputation will be applied for missing safety and efficacy evaluations. For analysis and reporting purpose, missing or partial dates in adverse event (AE onset date; AE end date), concomitant therapies (start date; end date), prior therapy (start date; end date), initial disease diagnosis date and start date of subsequent anticancer therapy will be imputed.

2.8.1. Missing/Partial Adverse Event Onset Date

If the onset date of an adverse event is missing completely or partially, the following imputation rules will be used.

- When month and year are present and the day is missing,
 - If the onset month and year are the same as the month and year of first study treatment, the day of first study treatment or the day-component of the AE end date (possibly imputed) is imputed, whichever is earlier
 - If the onset month and year are not the same as the month and year of first study treatment, then the first day of the month is imputed
- When only a year is present or no components of the onset date are present,
 - If the onset year is the same as the year of first study treatment. If AE end date is available and is prior to first study treatment, the day and month of AE end date are imputed. Otherwise, the day and month of first study treatment are imputed
 - If the onset year is different from the year of first study treatment, the 1st of January is imputed
- If the onset date is completely missing, the date of first study treatment is imputed as the onset date.

No imputation will be done for partial or missing AE onset time.

If AE onset date needs imputation, but the AE onset time is available, the AE onset time will be dropped in the imputed AE onset date/time variable.

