5.1. Adverse Events

All adverse events whether serious or non-serious, will be reported from the time a signed and dated ICF is obtained until 30 days after the last dose of study treatment, until the subject withdraws consent for study participation, or until the subject starts subsequent anticancer therapy, whichever occurs first. AEs will be recorded in standard medical terminology and graded according to the National Cancer Institute Common Terminology Criteria for Adverse Events (NCI-CTCAE), Version 4.03. For AE reporting, the verbatim term used in the CRF by investigators to identify adverse events will be coded using the latest version of Medical Dictionary for Regulatory Activities (MedDRA) coding dictionary.

Unless otherwise specified, at each level (e.g., system organ class and/or preferred term) of subject summarization in reporting the incidence of the AE, a subject is counted once if one or more events were recorded.

All summaries of AEs will be based on treatment-emergent adverse events (TEAEs). TEAEs are defined as any AE that occurs after start of the first study treatment through 30 days after the last study treatment; or the day prior to start of subsequent anticancer therapy, whichever is earlier; or any AE that is considered drug-related (very likely, probably, or possibly related) regardless of the start date of the event.

The incidence of TEAEs will be summarized overall, by MedDRA system organ class (SOC) and preferred term, by toxicity grade, and by relationship to study treatment administration. Specifically, the following AE summaries will be presented by NHL subtype:

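### SAP 2.8.1 covers a wholly missing AE onset date in two inconsistent bullets, and the only one that can be applied can date the onset after the AE's known end

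*SAP*

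**What the plan says.** SAP 2.8.1 sorts incomplete AE onset dates by what is known.

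- **Only the day missing, in the month of first dose.** The rule consults the end date: "the day of first study treatment or the day-component of the AE end date (possibly imputed) is imputed, whichever is earlier".
- **Only the year known.** The heading reads "When only a year is present or no components of the onset date are present", so it also takes in the wholly missing case. Its first sub-rule opens with "If the onset year is the same as the year of first study treatment" and continues "If AE end date is available and is prior to first study treatment, the day and month of AE end date are imputed"; failing that, the day and month of first dose are used. Its second sub-rule applies to a different onset year and gives 1 January.
- **Nothing known.** "If the onset date is completely missing, the date of first study treatment is imputed as the onset date".

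Where the date is imputed but a clock time was recorded, "the AE onset time will be dropped in the imputed AE onset date/time variable".

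SAP 5.1 collects AEs "from the time a signed and dated ICF is obtained" and bases all AE summaries on treatment-emergent events. By date, "TEAEs are defined as any AE that occurs after start of the first study treatment through 30 days after the last study treatment" (or up to the day before subsequent anticancer therapy, if earlier). Events judged drug-related also count, whatever their start date.

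**The concern.** Where part of the onset date is known and could coincide with first dose, 2.8.1 uses an end date before first dose to keep the event out of the treatment period. Where nothing about the onset is known, the end date is the only evidence of timing, and the operative bullet ignores it. The year-only heading claims the same case, so two programmers could reasonably produce different onset dates for one record.

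Such a record can arise. AEs are collected from consent and SAP 1.1 allows up to 28 days of screening, so an event can begin and resolve before first dose. At stake are a record with an impossible date order and, on one reading of the treatment-emergent definition, a resolved screening event in the AE tables. SAP section 1 adds some weight: if futility is met, this interim SAP becomes the study SAP, and the rule then governs the final safety report.

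**Working it through.** The plan states no figure to reproduce. The check applies the rules as written.

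**1. Can the year-only bullet handle a wholly missing onset?** Both of its sub-rules compare the onset year with the year of first dose. With no onset year, neither condition can be evaluated, so the end-date check inside the first is never reached. Only the last bullet can be executed.

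**2. Trace.** First dose is assumed to be 15 March 2016, for illustration only. The cells give the imputed onset.

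| Onset information | AE ends 1 March | AE ends 14 March | AE ends 20 March | End missing |
|---|---|---|---|---|
| Month and year (March 2016) | 1 March | 14 March | 15 March | 15 March |
| Year only (2016) | 1 March | 14 March | 15 March | 15 March |
| None, as written | **15 March** | **15 March** | 15 March | 15 March |
| None, with the end-date check | 1 March | 14 March | 15 March | 15 March |

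The two bold cells fall after the end of the event.

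**3. All end dates in screening.** Let D be the first-dose date and E an end date before it. The rule sets onset = D, so onset − end = D − E, which is at least 1 day. For the 28 days before first dose, 28 of 28 end dates give an onset after the end. With the end-date check, onset = E and the count is 0 of 28. Under the duration convention in SAP 2.1 (end minus start plus 1), the duration as written runs from −1 + 1 = 0 days (end the day before first dose) to −28 + 1 = −27 days (end 28 days before).

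**4. Is there a later repair?** SAP 2.8.1 and 2.8.2 contain none. SAP 2.8.3 and 2.8.4 re-adjust an imputed start that falls after the end for medications and prior therapies, and 2.8.6 does so for subsequent therapy.

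**5. Treatment-emergent status.** The imputed onset is D with no time. If an onset on D counts, all 28 records are treatment-emergent as written and none is with the check. If the onset must fall on a later date than D, none of the 28 qualifies by date. But then no AE imputed to D qualifies by date either, including those that end after first dose.

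**6. Size for one affected subject.** SAP 5.1 counts a subject once per preferred term, so the increment is 0 if that subject also has the same term after dosing. Otherwise it is 1/n:

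- DLBCL or FL Stage 1: 1/15 = 6.7 percentage points
- MCL Stage 1: 1/20 = 5.0 points
- DLBCL or FL with Stage 2 at the planned 55: 1/55 = 1.8 points
- MCL with Stage 2 at the planned 100: 1/100 = 1.0 point

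**The case against.** The strongest reply is that the affected set may be empty. It needs an AE with no onset day, month or year but a usable end date, falling between consent and first dose. Protocol 17.6 provides for review of the eCRF for completeness, with discrepancies resolved with the investigator, and an end date without even an onset year is an obvious query. This stands: the documents give no count and no basis for expecting one.

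It can also be said that the drafters did provide an end-date check, because the year-only heading names the wholly missing case. That stands as evidence of intent. It does not make the check usable, since the check hangs on an unknown year.

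Third, defaulting an unknown onset to first dose is conservative: it can only add treatment-emergent events. This also stands, and it is a good reason to keep the default wherever the end date does not contradict it.

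A reader might infer more than the text supports in three ways:

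- **That every such AE is certain to be counted as treatment-emergent.** The definition speaks of events after the start of first treatment, the imputed onset has no time, and the SAP does not say how a same-day, untimed onset is classed. Counting it is the likely implementation, but it is not written.
- **That the event enters the serious and grade 3/4 tables as a matter of course.** It does so only if it is serious or of that grade.
- **That 6.7 points is the expected effect.** It is the maximum for one subject in the smallest cohort.

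**Conclusion.** Wrong as written, and minor. One case is covered by two inconsistent bullets, and the one that can be executed gives an onset after the end for every AE with no onset information and an end before first dose. That result does not depend on how treatment-emergent is read.

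Counting the event as treatment-emergent is conditional. It assumes that an untimed onset on the first-dose date qualifies, which the SAP leaves open but which is the evident purpose of imputing that date. On that assumption, one affected subject adds between 0 and 6.7 points to a preferred-term incidence in a 15-subject cohort, and at most 5 points in MCL Stage 1. The number of such subjects is unknown and may be zero. The bias runs only towards overstating treatment-emergent AEs. The response rate and the futility rule do not use AE dates and are unaffected.

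**What to change.** Make two edits to SAP 2.8.1.

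1. Replace the last bullet with a rule to this effect: *Onset date wholly missing: if the AE end date (possibly imputed) is before the date of first study treatment, impute the AE end date; otherwise impute the date of first study treatment.*
2. Delete from the year-only heading the clause that brings in records with no date components, so that each case has one rule.

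Allowing an imputed end date matches the day-missing branch and is safe. SAP 2.8.2 fills a partial end date with the last day of the month or 31 December, capped at the date of death, so an imputed end before first dose means the true end was before it too. AEs with no end date, or one on or after first dose, keep the present default.

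The cost is one replaced sentence, one deleted clause and the matching line of derivation code. No new data are needed, and no AE with an unknown or on-treatment end is reclassified.

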2.8.2. Missing/Partial Adverse Event End Date

If the end date of an adverse event is missing completely or partially, the following imputation rules will be used.

- If month and year are present and the day of the month is missing, the last day of the month is imputed.
- If only a year is present, the 31st of December is used.
- If the imputed date is later than the date of death (if available), the date of death will be used as the imputed date instead.

No imputation will be done for partial or missing AE end time.

If AE end date needs imputation, but the AE end time is available, the AE end time will be dropped in the imputed AE end date/time variable.

2.8.3. Partial Concomitant Medication Start/End Date

In case of partially missing concomitant medication start/end dates, the following imputation rules will be applied. If the date is completely missing, no imputation will be performed.

- If only the day is missing, the 15th day of the month will be used
- If both the day and month are missing, the 30th of June will be used

If the medication was taken prior to study start, and the imputed start date is after first treatment date, further adjust the imputed start date as the day prior to first dosing date; if the medication was taken after study start, and the imputed start date is prior to first dosing date, further adjust the imputed start date as first dosing date.

After applying above adjusting method, if it results in medication start date that is after medication end date, the medication start date needs re-adjustment as follows:

If medication start date was imputed then adjust as follows:

- Impute the same month and year as medication end date if the non-imputed date parts are the same
- Impute the first day of the month as medication start day

If medication end date was imputed then re-adjust medication end date to be the same as the medication start date if the corresponding non-imputed date parts match the medication start date.

Also adjust the imputed medication end date so that it is on or after first dosing date.

2.8.4. Partial Prior Therapy Start/End Date

In case of partially missing dates, the imputation will be needed as follows. If the date is completely missing, no imputation will be performed.

Impute partially missing dates (start date, stop date) by using the following rules:

- If only the day is missing, the 15th day of the month will be used.
- If both the day and month are missing, the 30th of June will be used.

If the imputed start/end date is after first dosing date, further adjust the imputed start/end date as the day prior to first dosing date.

After applying above adjusting method, if it results in medication start date that is after medication end date, the medication start date needs re-adjustment as follows:

If medication start date was imputed then adjust as follows:

- Impute the same month and year as medication end date if the non-imputed date parts are the same
- Impute the first day of the month as medication start day

If medication end date was imputed then re-adjust medication end date to be the same as the medication start date if the corresponding non-imputed date parts match the medication start date.

2.8.5. Partial Initial Disease Diagnosis Date

For partially missing initial diagnosis dates, the following imputation rules will be applied. If the date is completely missing, no imputation will be performed.

- If only the day is missing:
 - If month and year of start of 1st line of prior NHL therapy are the same year and month of diagnosis, and day of start of 1st line of prior NHL therapy is available, impute day with day of start of 1st line of prior NHL therapy;
 - Otherwise, impute day with 15.
- If both the day and month are missing:
 - If year of diagnosis is the same as year of start of 1st line of prior NHL therapy, and month information is available for start of the 1st line of prior NHL therapy;
 - Impute month with month of start of 1st line of prior NHL therapy;
 - If day of start of 1st line of prior NHL therapy is available, impute diagnosis day with day of start of 1st line of prior NHL therapy; otherwise, impute diagnosis day with 15.
 - Otherwise, impute with June 30.

2.8.6. Partial Subsequent Anticancer Therapy Start Date

If year or month of subsequent anticancer therapy start date is missing or no components of the start date are present, no imputation will be performed.

If only the day-component is missing, the following steps apply:

- If the month and year of the start date are the same as the month and year of last dosing date, the day of last dosing date or the day-component of the stop date of subsequent anticancer therapy is imputed, whichever is earlier.
- If the start month and year are not the same as the month and year of last dosing date, the first day of the month is imputed.

If after the above imputation are applied, the imputed start date is after the non-imputed end date then re-adjust the start to be the same as the end date.

No imputation will be applied for missing or partial subsequent anticancer therapy end date.

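### SAP 2.8.6 and 2.8.1 compare day-numbers across different months, so an imputed therapy start can precede the last dose and an imputed AE onset can precede the first dose

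*SAP*

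**What the plan says.** SAP 2.8 states that several partial dates, including the "start date of subsequent anticancer therapy will be imputed", for analysis and reporting. Two of the rules matter here.

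- **2.8.6, therapy start with the day missing.** If the start month and year equal those of the last dose, "the day of last dosing date or the day-component of the stop date of subsequent anticancer therapy is imputed, whichever is earlier". For a start in a month that is "not the same as the month and year of last dosing date, the first day of the month is imputed". One check follows: if "the imputed start date is after the non-imputed end date then re-adjust the start to be the same as the end date".
- **2.8.1, AE onset with the day missing.** If the onset month and year equal those of the first dose, "the day of first study treatment or the day-component of the AE end date (possibly imputed) is imputed, whichever is earlier". No check follows.

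Two neighbouring rules are more careful. The year-only branch of 2.8.1 tests a full date: "If AE end date is available and is prior to first study treatment, the day and month of AE end date are imputed". Section 2.8.5 borrows a day only under a matching condition: "If month and year of start of 1st line of prior NHL therapy are the same year and month of diagnosis".

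**The concern.** Both rules check that the partial date shares month and year with the dose. Neither checks that the stop or end date does. A day-component is a day-number, and day-numbers from different months have no order in time. A date weeks after the dose can therefore pull the imputed date to before the dose.

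Three parts of the SAP use the results:

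- **5.1:** the treatment-emergent period opens at first study treatment and closes no later than the day before subsequent therapy. An onset placed too early falls out at the front, and a therapy start placed too early closes the period too soon. AEs judged drug-related count whatever their start date, so the loss is confined to AEs judged not related. For them the incidence can only go down.
- **2.1:** if there is no end-of-treatment visit date, the end of the last cycle also depends on the therapy start.
- **4.3.1:** PFS is censored at the last assessment before subsequent therapy.

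Section 1 makes this document the study SAP if futility is met, so these would then be the final safety tables.

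**Working it through.** The documents give no figure on this point, so there is none to reproduce. The check codes the rules and compares them with full-date versions.

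**Notation.** D is the dose date (last dose in 2.8.6, first dose in 2.8.1) and S the complete stop or end date. The partial date is in the month of D.

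- As written: imputed day = min(day of D, day of S), in the month of D. In 2.8.6 the result is then moved back to S if it is later than S.
- Full-date rule: imputed date = min(D, S).

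**Worked cases**

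| Rule | Dose | Partial date | Stop or end | As written | Full dates |
|---|---|---|---|---|---|
| 2.8.6 | 20 March | March | 10 March | 10 March | 10 March |
| 2.8.6 | 20 March | March | 25 March | 20 March | 20 March |
| 2.8.6 | 20 March | March | 4 May | **4 March** | 20 March |
| 2.8.1 | 20 March | March | 5 April | **5 March** | 20 March |

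The check in 2.8.6 does not act in the third case, because 4 March is not after 4 May. It corrects only a start that is too late.

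**When the rules differ.** If S is in the month of D, day-numbers and dates have the same order, so the two rules agree. If S is in a later month, S is after D and the full-date result is D. The rule as written gives an earlier date whenever the day of S is smaller than the day of D.

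**How often, per record with a complete stop or end date**

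- Idealised 30-day months, all pairs equally likely: 30 × 29 / 2 = 435 of 30 × 30 = 900 pairs, or 48.3%. The mean shift is 31 / 3 = 10.3 days.
- 2015 calendar, each date as D, each S in that month and the next 11:
  - same month: 0 of 11,111 differ;
  - later month: 59,094 of 122,420 = 48.3% differ, always before the dose, by 10.5 days on average.

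**How far this depends on equal likelihood**

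- 2.8.6: if therapy truly starts after the last dose in that month and lasts a fixed 7 to 180 days (assumed), the share among later-month stops averages 34%, ranging from 1% to 85% by duration.
- 2.8.1: if the AE truly starts on or after first dose in that month and has an exponential duration with mean 3, 7, 14 or 30 days (assumed), the share among AEs ending in a later month is 95%, 85%, 72% or 61%.
- AE end dates with the day missing seldom trigger the error, because 2.8.2 says "If month and year are present and the day of the month is missing, the last day of the month is imputed". With month-end dates, 47 of 4,380 pairs (1.1%) fall before the dose.

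**Effect on the treatment-emergent period.** In the 2.8.6 case the period closes on 3 March as written and on 19 March with full dates. AEs judged not related with onset on 4 to 19 March, 19 − 3 = 16 days, are lost. In the 2.8.1 case an AE still present after first dose is classed as starting 15 days before it.

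**Effect on PFS.** Read 4.3.1 as counting a progression only if it precedes the therapy start. With a later-month stop, the start is at or before the last dose under either rule. A progression on or after the last dose is then censored under both: over days 1 to 31 for last dose, stop and progression there are 31 × 496 = 15,376 such combinations, and event status differs in none. It differs only when progression was documented on or after the falsely early start and before the last dose.

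**Check of the remedy.** With the stop-date clause removed from 2.8.6 and its last sentence kept, the result equals the full-date rule in 133,531 of 133,531 pairs (11,111 + 122,420).

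**The case against.** The best reply is that the intent can be recovered. The year-only branch of 2.8.1, the closing check in 2.8.6 and the matching condition in 2.8.5 all handle dates properly, and a careful programmer may read the comparison as one of full dates. That is probably what was meant, but these two bullets do not say it, and the wrong result is a plausible day in the recorded month that no later check would catch.

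The second reply is that few records can qualify. The day must be missing with the month known, the month must be that of the dose, and the stop or end date must be complete, in a later month and with a smaller day-number. Stage 1 has 50 subjects, and Protocol 17.6 provides for review of the eCRFs for completeness. This stands and limits the importance of the point.

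Three stronger readings are tempting and not supported.

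- **That PFS is materially biased.** Protocol 9.1.3 has subjects stop treatment when progression is diagnosed, so progression normally falls on or after the last dose, where this error does not change event status. A censoring date moves only if an assessment falls in the short gap between the false start and the last dose, and SAP 1.1 schedules assessments 8, 16 and then 24 weeks apart.
- **That 5.1 should keep the window open at least to the last dose.** That would also override complete, correct start dates. The protocol's discontinuation criteria foresee non-protocol lymphoma treatment given concurrently, and 5.1 ends AE reporting when subsequent therapy starts.
- **That imputing the last-dose day or the first of the month is itself an error.** It is a stated convention for an unknown order. Even with full dates it closes the window the day before the last dose and can censor a progression later that month, but that is a separate question.

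**Conclusion.** The point holds as a drafting error in two imputation rules. As written, 2.8.6 and the day-missing branch of 2.8.1 can place a date before the dose when nothing recorded supports it. The error goes one way only and lowers the count of treatment-emergent AEs judged not related.

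Among records with a later-month stop or end date, about 48% are affected, by about 10 days on average, if all date pairs are equally likely. The share depends strongly on therapy and AE duration, as the ranges above show. It is not a share of subjects or of all AEs. The documents do not say how often days are missing, so the effect on the tables is unknown and probably small. PFS is a minor matter, and ORR and the futility count do not use these dates. The correction is worth making because it is cheap and this SAP may become the final one.

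**What to change.** - **2.8.6:** where the start month is that of the last dose, delete the alternative that uses the stop date's day-component, together with the closing words that pick the earlier of the two, so that the last-dose day alone is imputed. Keep the existing last sentence; it then gives the full-date result.
- **2.8.1, day missing, same month as first dose:** replace the rule with: *Use the AE end date only if that full date is before the first dose date; otherwise use the first dose date.*

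The definition of the treatment-emergent period in 5.1 and the PFS analysis need no change for this point.

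The cost is two short text edits and minor recoding. The one downside is that an AE that truly began earlier in that month, before first dose, but ended on or after it will be counted as treatment-emergent. For safety tables that is the cautious direction.
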